4.0 Study-Wide Number of Subjects

4.1 N/A

5.0 Study-Wide Recruitment Methods

N/A

6.0 Multi-Site Research

N/A

7.0 Study Timelines

7.1 *Describe:*

- *The duration of an individual subject's participation in the study.*
For participants in the BMT-Health group intervention – approx. 9 - 16 weeks from the date of screening/baseline enrollment
- *The duration anticipated to enroll all study subjects.*
Using a rolling recruitment approach, enrollment for the entire study is anticipated to take 2 years.
- *The estimated date for the investigators to complete this study (complete primary analyses)*
The estimated date for completion of this study is January 2020.

8.0 Study Endpoints

8.1 *Describe the primary and secondary study endpoints.*

The study endpoint is the completion of all subjects' participation in the study intervention and completion of all data collection and analysis.

8.2 *Describe any primary or secondary safety endpoints.*

N/A

9.0 Procedures Involved

9.1 *Describe and explain the study design.*

LEAP Group Intervention

At the beginning of the screening visit, informed consent/assent forms will be reviewed aloud with participants. Screening consists of completion of the K-SADS and physical activity screening questionnaire. Children eligible based on these measures will then complete PA tracking using accelerometer as described in section 3.1 Following screening into the

study and completing informed consent/assent and baseline study measures, caregivers will be assigned to an 8-week LEAP intervention group, with 6-8 caregivers per group. Children and caregivers will complete baseline and follow-up assessment batteries at 5 weeks and 9 weeks. Caregivers will participate in a 1-hour focus group regarding their experience in the intervention during week 9. PA will be measured using accelerometry x7 days at baseline and at 9 weeks. The LEAP intervention consists of 3 components: 1) an enhanced 8-week, group-based BMT curriculum, 2) caregiver and child use of the Garmin daily activity tracker accompanied by personalized goal setting, and 3) caregiver participation in a private Facebook group to encourage PA goal achievement and promote social support and positive parenting. All enrolled families will receive 8 weekly group BMT-Health sessions led by either [name] or [name], who have considerable experience leading BMT groups for children with ADHD. Groups will include initial enrollment of 6-8 families, a group facilitator, and a co-facilitator. The curriculum and homework is based on existing evidence-based models, namely Barkley's Defiant Children¹² curriculum, with integrated content specifically focused on promoting PA and addressing barriers to PA. Table 1 presents a sampling of session content, highlighting the unique aspects of the BMT-Health curriculum compared to standard BMT. Later sessions (with related homework) will include topics such as: community resources for PA, challenges encountered and over-coming barriers, using incentives to promote healthy behaviors, role of bedtime routines/sleep, and goal-setting for the future/strategies for sustainability. Information and resources relevant to that week's topic will also be provided via Facebook and text messages. Fidelity to the curriculum will be assessed by trained coders using content checklists in a randomly-selected sampling of session audiotapes. We included the standard Barkley curriculum with this IRB application. We now include an overview of LEAP curriculum sessions 1-8 and how the sessions are similar to and differ from the Barkley curriculum (see separate attachment).

Table 1. BMT Standard and BMT-Health Curricula Overview – Sessions 1-3.

Barkley's Defiant Children¹²					
Strategy Instruction	Homework	Session	BMT-Health		
			Unique Strategy Instruction	Unique Homework	Unique Targets

 Psychoeducation: ADHD and causes of child misbehavior Teach differential attending and "special time" strategies 	
 Daily "special time" play 	1	
 Psychoeducation: ADHD/misbehavior and connections with PA and health behaviors Teach incorporation of active play into daily "special time" Distribute and teach caregivers to use Garmins 	
 Daily "special time" with active play Caregiver & child wear Garmin 	
 Child and caregiver engage in active (Non-sedentary) play together Child and caregiver monitor activity levels
			
 Discuss PA successes. Identify and problem-solve barriers. Teach caregiver self-care strategies (e.g., own PA, sleep, 	
 Set individual child and caregiver PA goals based on prior week's Garmin results 	
 Establish individualized goals for PA Increase

compliance	compliance		self-talk, social support) • Introduce caregiver Facebook group	• Join and participate in Facebook group	caregiver PA and social support via Facebook group
• Teach effective commands and limit setting (i.e., rules, when/then commands, timers)	• Use effective commands, limit setting strategies	3	• Teach limit setting strategies applied to PA and rules for media use • Psychoeducation: media use and ADHD	• Develop and implement family media use plan • Use effective limit setting to support family media use plan	• Reduce child and caregiver media use • Replace sedentary activity with active play

9.2 Provide a description of all research procedures being performed and when they are performed, including procedures being performed to monitor subjects for safety or minimize risks. Please be clear about how the procedures performed differ from standard of care. If procedures preclude or delay standard of care, please be sure to include this information.

Garmin Wrist-worn Activity Tracker – Vivofit Jr; The Garmin vívofit jr is a wrist worn activity tracker intended for children ages 4 to 9 years old. It has a 1+ year battery life, is waterproof, and tracks steps and PA with a built in tri-axial accelerometer. The child-friendly displays shows step count and whether the "activity goal" of >60 minutes was met. Caregivers can use a compatible application on their Apple or Android smartphone to monitor the activity of up to 8 family members. The device can store data for 4 weeks. For the caregivers, we will use an adult oriented wrist-worn product, the Garmin vívofit4, which has a 1+ year battery life and a digital display with steps, PA duration and intensity, and a "move bar" which alerts them to move. Participants will be encouraged and supported in setting personalized goals based on their actual PA data collected by the Garmin in week 1 and incrementally increase activity to meet and maintain population recommendations for their age. Using a texting platform, we will set up automated weekly texts to go out to participating caregivers with reminders and goals. The content of the texts will be submitted to the IRB prior for review prior to using them in the study. The weekly texts will continue until the last data collection period at each phase of the study. Intervention participants will be encouraged to share their Garmin data on their own personal social media profile with their online friends and other study participants. Participants will also receive brief health coaching regarding PA goal setting each week with study staff, which has been found to be effective in other PA interventions.⁹

BMT group based curriculum - BMT programs – such as Barkley's Defiant Children¹² – are front-line treatments for childhood ADHD,¹³ and focus on issues such as reducing noncompliance and parenting stress. We propose to enhance Barkley's program to target PA via BMT strategies such as special time, praise, and incentive systems, which we hypothesize will increase PA and yield greater improvements in ADHD symptoms and

functioning than existing BMT programs or stand-alone interventions providing structured PA sessions.

Facebook Group.

We will create a private (invitation only) Facebook group for each LEAP intervention group to provide encouraging advice and messages to promote PA, announce weekly individual and group badges/awards (e.g., most improved, most steps, most active minutes, most Facebook posts, etc.), and to provide a forum for participants to discuss PA and use of the Garmin devices. A group facilitator profile will be created with which research assistants can post to the group page, interact with participants, and screen content posted by members daily to remove it if inappropriate. The facilitator will make about 5 posts per week providing encouragement, reminders and study procedures, and opportunities to troubleshoot and answer questions. We have included a manual with information on planned posts. Participants will earn digital badges for meeting their weekly activity goals, as well as for social interactions (e.g. "liking" other's posts) or making improvement toward goals to ensure that all participants receive positive feedback. We will begin the first 4 weeks with badges awarded to individuals only (e.g. most improved individual, most steps (from baseline) for an individual, etc.). Starting in week 5, we will award additional badges contingent on the entire intervention group meeting pre-specified criteria (e.g. 250,000 steps attained). This "all for one and one for all" approach is designed to foster encouragement and cooperation among the participants to promote PA and to keep participants engaged. Participants will be encouraged but not required to post in the group and to encourage their fellow participants. Participants will also receive standardized weekly text messages (using a free service) reminding them to wear/sync their Garmin and increase PA in their family routines. The facilitator and investigators will build upon the operations manual used in our teen ADHD pilot study to add practical information and troubleshooting tips for the purposes of training and guiding others to fulfill the role as independently as possible. Facilitator will track time spent each week as an indicator of implementation burden.

Questionnaires/Measures – listed in Table 2; completed by teachers, caregivers, child participants, or therapists. Of the measures listed below, we will submit the HBD for IRB approval prior to administration.

- Hip –worn Accelerometer – Actigraph model GT3X+; A small rectangular device housing a tri-axial accelerometer and worn on an elastic belt, the GT3X+ has been used in a number of studies conducted by [name] (Co-PI) research group and a number of other research groups at Seattle Children's. Children will be asked to wear the device with an elastic belt for 7 days on their hip. In order to maximize valid accelerometer data, participants will be asked to wear accelerometers for 24 hours/day, except for water-based activities,[38] and to re-wear accelerometers for another 7-day period if they have < 4 valid days at each measurement time point. The 24-hr wear has been validated for use to collect sleep data in school age

children, which is an exploratory outcome in this study.[39] While sleep has traditionally been measured with wrist actigraphy, algorithms have been produced, validated, and refined to fully automate the capture of sleep duration for children using 24-hour waist-worn accelerometry.[40] As we plan to use a 24-hour waist-worn accelerometer protocol to maximize compliance for the PA data, we will also be able to capture quantitative sleep data on our participants for a broader perspective on these related health behaviors.

Digit Span task asks children to repeat strings of numbers of increasing length forward, then backwards.

- *Stop Signal Reaction Time (SSRT):* In this computerized task, the participant must respond to an arrow stimulus, by selecting one of two options, depending on the direction in which the arrow points. If an audio tone is present, the subject must withhold making that response (inhibition). The test consists of two parts: In the first part, the participant is introduced to the test and told to select the left-hand button when they see a left-pointing arrow and the right-hand button when they see a right-pointing arrow. There is one block of 16 trials for the participant to practice this. In the second part, the participant is told to continue selecting the buttons when they see the arrows but, if they hear an auditory signal (a beep), they should withhold their response and not select the button. The total task requires 15-20 minutes to complete.

Table 2 – Study Measures and Assessments

Construct	Measure	Rater	Source	Screening	Baseline	5 weeks	9 weeks
ADHD diagnosis	K-SADS-PL	P/C	CR	X			
ADHD severity	CGI-S	Clinician	CR	X			X
PA, Sleep	MVPA, light & sedentary time, Step count, sleep duration x 7 days	G/C/A	E		X		X
Feasibility	Garmin (wear time), Facebook likes and comments	G/P/C	E, SE			X	X
Acceptability	Attendance, TAI	P	CR, DP			X	X
Acceptability	CSQ, Focus group		DP				X
Executive function	SSRT, DS, BRIEF-2	C/P	SE		X		X
ADHD symptoms	Conners-3 (P), Vanderbilt (T)	P/T	DP		X		X
Functional impairment	IRS	P/T	DP		X		X
Parenting	APQ	P	DP		X		X
PA, Sleep, Media use	HBS	P	DP		X	X	X
Sleep problems	CSHQ	P	DP		X		X
BMI	Height, weight	C	SE		X		X
Complementary/Alternative medicine use	HBS	P	DP		X		X
Media Use	Problematic Media Use	P	DP		X		X
Medication use	HBS	P	DP		X	X	X
Mindfulness	Mindful Attention Awareness		DP		X	X	X

	Scale							
Socio-demographics	Survey	P	DP			X		

APQ = *Alabama Parenting Questionnaire*. BMI = *Body Mass Index*. BRIEF = *Behavior Rating Inventory of Executive Function*. CGI-S = *Clinician Global Impressions Scale – Severity*. Conners-3 = *Conners-Third Edition*. CSHQ = *Children's Sleep Habit Questionnaire*. CSQ = *Client Satisfaction Questionnaire*. DS = *Digit Span task*. ERC = *Emotion Regulation Checklist*. FW = *Finger Windows task*. HBS = *Health Behaviors Survey*. IRS = *Impairment Rating Scale*. K-SADS-PL = *Kidnie-SADS-Present and Lifetime Version*. MVPA = *Moderate-to-Vigorous Physical Activity*; PA = *Physical Activity*. SSRT = *Stop-Signal Reaction Time task*. TAI = *Treatment Adherence Inventory*. A = *Actigraph GT3x+*; C = *Child*; G = *Garmin Device*; P = *Parent*; T = *Teacher*. DP=digitally entered by parent/caregiver; CR=Clinician rated; E=electronic device data; SE =study staff entered

For the K-SADS instrument:

- the Pregnancy and Birth Questions will not be included
- the Family History for Biological Relatives will not be included

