11.0 Data Analysis/Management

Describe the data analysis plan, including any statistical procedures.

Given the pilot nature of the R21 study, data analysis will be largely descriptive and exploratory. We will focus on parameter estimates instead of formal hypothesis testing. The feasibility and acceptability of the research protocol as outlined above is the main outcome of interest, as is now recommended for pilot studies, rather than effect size estimates.¹⁰⁹

Study aim 1: To test the feasibility and acceptability of the intervention

Feasibility will be assessed by (a) demand through inquiry and enrollment rates and (b) practicality and participation through attrition rates and adherence with intervention (attendance, percentage of days wearing and syncing Garmin, participation in Facebook group) and study procedures (screening, follow-up batteries, accelerometry).

Acceptability will be assessed through participant ratings and qualitative interviews.

Fidelity of the social media/text component will be evaluated following a procedure for prior mHealth intervention pilots conducted by the study team including tracking facilitator posts, participant views, likes, and posts. We will summarize the measures listed above using means, medians, and standard deviations for continuous variables and proportions for categorical variables and then conduct bivariate analyses. Non-parametric tests will be used on non-normally distributed continuous variables, and Fisher's exact test on sparse categorical variables. The proportions that reflect acceptability and feasibility will be assessed using 95% exact (Clopper-Pearson) confidence intervals

Exploratory Aim: To explore the effects of the intervention on PA

We will compare within-subject pre to post activity using accelerometer data (step count; sedentary, light and MVPA; sleep duration), MVPA as an exploratory outcome. We will examine gender as an effect modifier given that differences in PA are seen between boys and girls from an early age and differential effects of previous PA interventions by gender have been noted.(111) We will also look at associations of the measures from Aim 1 with PA outcomes. Pre- and post-intervention outcomes will be compared using t-

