14.0 Withdrawal of Subjects

14.1 *Describe anticipated circumstances under which subjects will be withdrawn from the research without their consent.*

We do not anticipate conditions where subjects will be withdrawn from the research without their consent.

14.2 *Describe any procedures for orderly termination.* N/A

14.3 *Describe procedures that will be followed when subjects withdraw from the research, including partial withdrawal from procedures with continued data collection.*

Should subjects withdraw from the research, we will keep their data (unless requested otherwise from subject) for later analyses. Like all other data to be analyzed, subjects who withdraw will have their data de-identified and kept on HIPAA compliant servers. As much as possible, we will remove content posted by the participant from the Facebook group and direct the participant to delete the Garmin app.

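### Satisfaction is asked about only at week 9, with no exit rating from families who stop earlier, so acceptability may be overstated if dissatisfied families leave

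*Combined protocol and SAP*

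**What the plan says.** Acceptability is named with feasibility in Aim 1 (section 1.1) and in the hypothesis (section 1.2). Section 11 makes the two together the main outcome, ahead of effect-size estimates.

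On measurement, section 11 says: "Acceptability will be assessed through participant ratings and qualitative interviews". On analysis it says: "The proportions that reflect acceptability and feasibility will be assessed using 95% exact (Clopper-Pearson) confidence intervals".

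Table 2 (section 9.2) has two acceptability rows:
- "Attendance, TAI", marked at 5 weeks and 9 weeks. TAI is the Treatment Adherence Inventory.
- "CSQ, Focus group", with a single mark, at 9 weeks. CSQ is the Client Satisfaction Questionnaire, coded as entered digitally by the caregiver.

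Section 9.1 confirms the timing of the second row for the focus group: "Caregivers will participate in a 1-hour focus group regarding their experience in the intervention during week 9".

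The plan allows for dropout. Under feasibility, section 11 lists "practicality and participation through attrition rates". For families who leave, section 14.3 says "Should subjects withdraw from the research, we will keep their data" unless they ask otherwise, and then deals with their Facebook content and the Garmin app. It provides for no exit questionnaire, no exit interview and no recorded reason for leaving.

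The documents give no denominator or missing-data rule for acceptability proportions, no CSQ score that counts as satisfied, no acceptability target and no expected attrition rate.

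**The concern.** A satisfaction rating taken once, after the last session, is observed only in families still willing to answer then. If disliking the program is one reason for leaving, the families who would rate it lowest are the ones most likely to have no rating. The responder proportion then describes a group selected toward satisfaction. The exact confidence interval around it reflects sampling error among responders and says nothing about the families who are absent.

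The other recorded items do not fill the gap. Attendance and attrition show that a family stayed away. They do not separate a family that found the program unacceptable from one that had a transport or scheduling problem. The TAI is by its name a measure of adherence; its items are not shown. A family that leaves before week 5 may have no TAI either.

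The stake is the main product of the study. With no comparator and no confirmatory test, the acceptability estimate is a large part of what a later trial would build on.

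**Working it through.** The plan has no acceptability calculation to reproduce, so the check is an illustration of how far a responder figure can sit from the figure for all families.

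**Inputs**
- Families enrolled: N = 30 (sections 11.1 and 25.0). I assume that all 30 start a group.
- Interval method: 95% Clopper-Pearson (section 11).
- Families with no week-9 rating: m = 0, 3, 6 or 9. Assumed.
- Proportion of responders satisfied: about 90%, rounded to whole families. Assumed, as is the satisfied/not satisfied cut-off itself.

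**Formulas**
- With p_R the proportion satisfied among responders and p_M that among missing families, the proportion over all families is p_all = [(N − m)·p_R + m·p_M] / N.
- The overstatement is therefore p_R − p_all = (m/N)·(p_R − p_M). It is zero if nobody is missing or if missing families are as satisfied as responders.
- The bounds follow from p_M = 0 and p_M = 1. The distance between them is m/N.
- Clopper-Pearson limits for x of n: lower = Beta(0.025; x, n − x + 1), upper = Beta(0.975; x + 1, n − x).

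**Bounds over the assumed range of missing families**

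| Missing | Responders satisfied | All 30, missing counted as not satisfied | All 30, missing counted as satisfied |
|---|---|---|---|
| 0 | 27/30 = 90.0% | 90.0% | 90.0% |
| 3 | 24/27 = 88.9% | 24/30 = 80.0% | 27/30 = 90.0% |
| 6 | 22/24 = 91.7% | 22/30 = 73.3% | 28/30 = 93.3% |
| 9 | 19/21 = 90.5% | 19/30 = 63.3% | 28/30 = 93.3% |

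**Overstatement with 6 missing (m/N = 0.20)**
- None of the 6 satisfied: 0.20 × (0.917 − 0) = 0.183, or 18.3 points.
- Half satisfied (25/30 = 83.3%): 0.20 × (0.917 − 0.500) = 0.083, or 8.3 points.
- Five of 6 satisfied (27/30 = 90.0%): 0.20 × (0.917 − 0.833) = 0.017, or 1.7 points.
- All 6 satisfied (28/30 = 93.3%): 0.20 × (0.917 − 1) = −0.017, a slight understatement.

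**Exact 95% intervals with 6 missing**
- Responders, 22/24: 73.0% to 99.0%.
- All families, lower bound, 22/30: 54.1% to 87.7%.
- All families, upper bound, 28/30: 77.9% to 99.2%.

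The responder interval stops at 73%. Once the missing families are allowed for, the lower limit could be 54%.

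**The case against.** The strongest reply is that acceptability is not measured only at week 9. Table 2 lists attendance and the TAI as acceptability measures at week 5 as well, and attendance can be counted for every family that starts, including one that leaves at week 3. This stands, and a reader who took the plan to measure acceptability in completers alone would be wrong. What is confined to week 9 is the direct expression of opinion.

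Second, dropout is not hidden: attrition is an Aim 1 outcome and would be reported beside the satisfaction results. This also stands. It tells the reader how many left, but not what they thought.

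Third, one might infer that families who stop will be largely absent at week 9 and that acceptability will be overstated. The documents do not support either statement. The week-9 battery in section 9.1 is not restricted to attenders, the CSQ is completed digitally, and section 23.4 pays $50 for week 9 and $15 for the focus group. Some families who stopped sessions may well respond. No attrition rate is given, and families can leave for reasons unrelated to dissatisfaction. Only those who withdraw or do not respond are lost, and the direction and size of any bias depend on their views.

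Fourth, section 11 refers to interviews without giving a time, so some qualitative data could in principle come from elsewhere. The only qualitative contact with caregivers about their experience that is actually scheduled is the week-9 focus group.

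Finally, this is a descriptive pilot with no acceptability threshold, so no pre-set decision turns on the difference. That limits the consequences. It does not remove the risk to the estimate.

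**Conclusion.** The point holds as a gap in data collection and reporting. The CSQ and focus group are scheduled only at week 9, no satisfaction rating or reason is sought from families who stop or withdraw earlier, and no denominator is set. Acceptability may be overstated if dissatisfied families leave early.

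The size cannot be derived from the documents. Under the assumed 6 of 30 missing and an assumed cut-off, the overstatement runs from about 18 points if none of the missing families was satisfied to about 2 points if five of six were. It vanishes with complete follow-up. None of these percentages is a figure that the plan itself commits to. This is a worthwhile, low-cost improvement; it does not invalidate the design.

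**What to change.** - When a family stops attending or withdraws, send the caregiver the existing digital CSQ with one added item on the reason for stopping. Add this to section 14.3 and Table 2.
- State that families who stopped sessions but have not withdrawn from the research will be invited to the week-9 battery.
- In section 11, report acceptability over all families who started a group, beside the responder figure, with bounds that count non-responders first as not satisfied and then as satisfied. Define in advance the CSQ score that counts as satisfied.

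The cost is one short extra form for families who stop, its submission for ethics approval, and a few lines of protocol text. No extra visit is needed. Some families who leave will not answer, so the bounds remain necessary, and the headline figure may be less favourable.
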